22.5 Protocol Deviations

Deviations occur when the investigators, study staff, or participants fail to adhere to protocol requirements or when there is non-adherence to GCP guidelines.

Upon determination that a protocol deviation has occurred, the study staff will notify the Principal Investigator promptly. Substantive protocol deviations from the protocol that affect rights, safety or welfare of participants , their willingness to continue in the study or impact the integrity of the research data will be reported promptly to the IRB per IRB regulations.

23. Provisions to Protect the Privacy Interest of Participants

A participant's privacy and confidentiality will be respected throughout the study. Each participant will be assigned a unique patient identification number (PTID) and these numbers rather than names will be used to collect and store participant information and samples. A file linking the participant identity, i.e., name, to their unique study participant ID (PTID) is maintained at the Hope Clinic in a separate locked file cabinet and on a HIPAA compliant clinical management database. Screening, consenting, and study visits will take place in private clinic rooms.

Any publications from this study will not use information that will identify participants by name or PTID. A description of this trial will be available on <http://www.ClinicalTrials.gov>, as required by US Law. This web site will not include information that can identify participants. At most, this web site will include a summary of the results. Site personnel will only transmit documents containing personal identifiable information (PII) using encrypted email or fax in accordance with HIPAA regulations (e.g., to send/receive safety lab data and medical records to/from primary care provider).

24. Economic Burden to Participants

There is no cost to participants for the research tests, procedures, or study product while taking part in this study. Procedures and treatment for clinical care may be billed to the participant, participant's insurance or third party. Participants may be compensated for their participation in this study. Compensation will be in accordance with the local IRB policies and procedures, and participant to IRB approval.

If it is determined by the principal investigator that an injury occurred to a participant as a direct result of the tests, procedures or treatments that are done for this study, then referrals to appropriate health care facilities will be provided to the participant. Study personnel will try to reduce, control, and treat any complications from this study. Immediate medical treatment may be provided by the participating site. No financial compensation will be provided to the participant for any injury suffered due to participation in this study.

25. Informed Consent

25.1 Statement of Compliance

This study was designed to ensure the protection of participants according to the ethical principles of the Declaration of Helsinki and amendments concerning medical research in human participants. This clinical study will be conducted using current good clinical practice and according to the criteria specified in this study protocol. Before study initiation, the protocol and the informed consent documents will be reviewed and approved by the IRB, as well as any other appropriate health authorities. Any amendments to the protocol or to the consent materials will also be approved by the appropriate bodies listed above prior to implementation.

25.2 Informed Consent Process

The informed consent form will provide information about the study to a prospective participant to allow for an informed decision about participation in the study. Prospective participants must be given ample opportunity to review the informed consent and inquire about the results of the study. The consent form will be provided electronically to the prospective participant during the first screening phone call. A copy of the informed consent form will again be provided to a participant for review prior to any study procedure during the in person screening visit. The Principal Investigator or an approved designee will discuss the consent with the prospective participant and answer questions. Study staff will read through the consent form with potential participants and answer any questions. Participants will be allowed sufficient time to consider participation in the study, after having the nature and risks of the trial explained to them and have the opportunity to discuss the trial with their family, friends. The prospective participant will be told that being in the study is voluntary and that he or she may withdraw from the study at any time, for any reason. The consenting process will take place in private exam rooms at the Hope Clinic. We anticipate that the consent process will take about 30-60 minutes.

All participants must read, sign, and date a consent form before undergoing any study procedures. Consent materials will be provided in the English language, however, shortforms and a qualified interpreter are available and IRB approval will be requested for use in consenting non-English speaking participants. A copy of the signed consent form will be given to the participant. The informed consent form will be revised and receive IRB approval whenever important new safety information is available, whenever the protocol is amended, and/or whenever any new information becomes available that may affect participation in the study.

Participants will be compensated for their time and travel. The informed consent form will specify the amount of compensation for each participant.

26. Setting

Potential participants will be recruited and screened from the general population of metro Atlanta. Participants will be enrolled at the Hope Clinic, Decatur, Georgia.

27. Resources Available

The Hope Clinic has a database of more than 5000 previous volunteers who can be considered for screening for the study. The Hope Clinic also has a website and the ability to reach out to potential participants through advertising around the Emory University campus.

27.1 Facilities

The Hope Clinic is a community-based vaccine research clinic and is the clinical arm of the Emory Vaccine Center. The Winship Cancer Institute is the only National Cancer Institute–Designated Comprehensive Cancer Center in Georgia and one of only 50 in the country.

27.2 Participant Support

Referrals to appropriate medical or psychological health care facilities will be provided by the investigators to the participant as needed due to the anticipated consequences of human research. Study personnel will try to reduce, control, and treat any complications from this study. Immediate medical treatment may be provided by the relevant site (Hope Clinic or Winship).

Appendix A. Schedule of Procedures

	-60 to -32	-31 to -29	1	2	4	8± 1	15 ±2	29± 3	91± 7	181 ±15	Phone call^
	V 1	V2	V3	V4	V5	V6	V7	V8	V9	V10	
Informed consent	x										
Demographics, medical history	x										
Interim medical history		x	x	x	x	x	x	x	x	x	x
Medications	x	x	x	x	x	x	x	x	x	x	x
Targeted physical exam	(x)	(x)	(x)	(x)	(x)	(x)	(x)	(x)	(x)	(x)	
Vital signs	(x)	(x)	(x)	(x)	(x)	(x)	(x)	(x)	(x)	(x)	
Blood draw for screening	x										
Stool Sample collection		x	x					x			
Pregnancy test (if applicable)	x		x	(x)	(x)	(x)	(x)	(x)	(x)	(x)	
Vaccination			x								
Statin therapy*		x	x	x	x	x	x	x			
Memory Aid			x	x	x						
Blood draw for immunological assays	x	x	x	x	x	x	x	x	x	x	
Clinical labs for statin therapy	x		x					x			
Adverse events		x	x	x	x	x	x	x			x
Serious adverse events		x	x	x	x	x	x	x	x	x	

Conducting a visit outside window is allowed at investigator discretion

Parentheses indicate a given procedure will be conducted if relevant for the visit: vital signs and pregnancy testing if applicable will be on the day of screening, prior to statin therapy initiation and prior to vaccination.

*Each participant receiving statin therapy will have clinical labs drawn. The tests conducted will be: Lipid profile, Creatinine Phosphokinase, Liver function tests, CRP. These tests will be valid for 30 days.

[^]phone call is completed 15 days after initiation of statin therapy.

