6.1 Screening and Consenting (D-60 to D-32)

6.1.1 Potential participants interested in the study will respond to study ads. Recruiters from the Hope Clinic will then contact them for a telephone screening, during which the research study will be explained in lay terms and eligibility criteria will be reviewed. If all eligibility criteria are met and the participant remains interested, an in-person screening appointment will be scheduled. Prior participants in other studies conducted at the Hope Clinic, and who had indicated their willingness to participate in other studies may also be contacted for a telephone screening visit.

6.1.2 At the in-person screening appointment , study staff will review the informed consent form with the participant and will answer all questions related to the study. Once the participant signs the informed consent, they will be assigned a unique study participation number. The following procedures will be performed:

- Recording of demographic information and review of medical history including recent influenza infection, including current medication use (medications that may interact with Atorvastatin) and vaccination history (previous receipt of influenza vaccines).
- Vital signs and targeted physical exam as indicated based on review of participant health status.
- A urine pregnancy test will be performed if the participant is a woman of child-bearing potential.
- Blood sample collection for baseline immunological assays and baseline clinical labs. Clinical labs may be repeated at investigator discretion.

6.1.3 Participants who remain eligible for the study will be randomized to either Statin therapy + QIV arm or QIV alone arm. Participants randomized to the Statin therapy+ QIV arm will receive the Atorvastatin pills with clear instructions on how to use them in a separate visit.

6.1.4 Clinical staff wil provide participants with a stool collection kit along with an information sheet explaining how the stool collection is done. The steps will be explained to the participant who will be asked to provide a stool sample on D-31, D1, and D29.

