6.2 Initiation of Statin therapy (D-31 to D-29)

Participants randomized to the Statin + QIV arm will be asked to come back to the Hope Clinic for an extra visit one month prior to date of vaccination. The following procedures will be performed:

- Review of interim medical history for any updates or changes.
- Review of concomitant medications for any updates or changes.
- Recording of vital signs and targeted physical exam if indicated.
- Blood sample collection.
- Stool sample collection.
- Re-verification of eligibility criteria.
- Completion of prescription form by licenced provider and dispension of Atorvastatin 80mg by the pharmacy at the clinic.
- Distribution of the drug to participant by study coordinator or nurse or provider with clear instructions on modalities of administration of the drug and common side-effects.

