6.4 Vaccination Visit (D1)

The following actions will be performed on the day of vaccination:

- Review of inclusion and exclusion criteria to confirm eligibility.
- Review of medical history, concomitant medications and vaccinations.
- Collection of vital signs.
- Completion of a targeted physical exam if needed.
- For participants of child-bearing potential, a negative urine pregnancy test is required.
- For the statin therapy group, participant compliance to the drug will be assessed.
- Blood samples for immunologic assays will be collected prior to vaccination
- Stool sample collection
- Participants will receive the CDC influenza vaccine information sheet and review it prior to vaccination.
- Participants will then receive QIV via the intramuscular route, administered by a clinical research nurse or provider.
- Participants will be observed for a minimum of 15 minutes for any immediate hypersensitivity reactions.
- Participants will be asked to fill a memory aid for 7 days after vaccination. Participants will have the option of an online survey or paper memory aid.

The visit will last approximately 60 minutes.

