In keeping with NIH policy on scientific data sharing, gene expression (RNA sequencing) data and immunological assay results will be made publicly available through public database deposition and peer-reviewed publication. Participants will be fully de-identified (i.e., disseminated data will not contain direct identifiable information). Demographic data (e.g., age, race and/or ethnicity, sex/gender) associated with participants will be kept strictly separate from all experimental results, including gene expression data. This practice has become standard to protect participant privacy.

9. Sharing of Results with Participants

Laboratory results

Immunologic assay or omics results will not be reported to participants as these are intended for research purposes only and therefore cannot be reported to patients per Clinical Laboratory Improvement Amendment (CLIA) regulations.

The results from safety laboratory tests conducted prior to statin therapy can be shared with participants.

Incidental findings

Incidental findings that appear in the results of the safety labs drawn will be disclosed and explained to the participant by the study investigator, who will provide a referral to the appropriate clinical specialist and information on how to obtain health insurance to secure treatment if needed. The study investigator will also send a message to the participant's primary care provider requesting follow-up with the participant if the participant authorizes this and provides relevant contact information.

10. Study Timelines

Individuals will participate in this study for a total of 8 months. Recruitment of all participants will require 24 months. The study and data analysis should be concluded within 48 months of start date.

11. Inclusion and Exclusion Criteria

Inclusion Criteria

1. Able to understand and give informed consent.
2. Age 18-50 years.
3. Women of child bearing potential must agree to use effective birth control for the first 3 months of the study. A negative urine pregnancy test must be documented prior to vaccination.

Exclusion Criteria for All Participants

1. History of allergy or serious adverse reaction, including Guillain-Barré syndrome, to a vaccine or vaccine products.

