2. History of a medical condition resulting in impaired immunity such as active solid tumors, leukemia, lymphoma, use of immunosuppressive drugs, chemotherapy or radiation therapy. Persons with previous skin cancers or cured non-lymphatic tumors are not excluded from the study.
3. History of HIV, Hepatitis B or Hepatitis C infection.
4. Chronic clinically significant medical problems that could be considered active or unstable (i.e diagnosed within the past 3 months or requiring a change in medication within the past 3 months). This is including (but not limited to):
 - a. Insulin dependent diabetes

- b. Severe heart disease (including arrhythmias)
- c. Severe lung disease
- d. Severe liver disease
- e. Severe kidney disease
- f. Severe hypertension: defined as life-threatening consequences (e.g., malignant hypertension, transient or permanent neurologic deficit).
- 5. BMI > 30
- 6. Current or previous use of statins or any other lipid-lowering drug.
- 7. Pregnancy or breast feeding, or plans to become pregnant in the first 3 months of study participation.
- 8. History of influenza infection within the same influenza season.
- 9. Receipt of blood products or immune globulin product within the prior 3 months.
- 10. History of excessive alcohol consumption, drug use, psychiatric conditions, social conditions or occupational conditions that in the opinion of the investigator would preclude compliance with the trial.
- 11. Receipt of any live vaccines 30 days before, or plans to receive any live vaccines 30 days after vaccination.
- 12. Receipt of any inactivated vaccines 14 days before, or plans to receive any inactivated vaccines 14 days after vaccination.

For participants randomized to the statin therapy+QIV group:

- 1. Participant is currently taking any medication that has known interactions with statin therapy.
- 2. History of renal or hepatic impairment.
- 3. Safety lab results showing:
 - a. CPK \geq 1.5 ULN
 - b. AST \geq 1.5 ULN
 - c. ALT \geq 1.5 ULN
 - d. LDL \geq 160 mg/dL

12. Population

HMG-CoA reductase inhibitors decrease cholesterol synthesis and possibly the synthesis of other biologically active substances derived from cholesterol. This may cause fetal harm when administered to pregnant female. Pregnant women are also excluded from the study as their immune responses after vaccination will differ from the general population.

13. Vulnerable Populations

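### Appendix A's footnote calls for a pregnancy test before atorvastatin is started, but the schedule grid and the Section 6.2 visit list both leave it out

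*Combined protocol and SAP*

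**What the plan says.** The Appendix A footnote covers vital signs and pregnancy testing in one sentence and states that "pregnancy testing if applicable will be on the day of screening, prior to statin therapy initiation and prior to vaccination".

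Two of the three occasions are repeated in the procedure text. Section 6.1.2 (screening) says: "A urine pregnancy test will be performed if the participant is a woman of child-bearing potential". Section 6.4 (vaccination, D1) says: "For participants of child-bearing potential, a negative urine pregnancy test is required".

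Section 6.2 describes the visit at which the statin is prescribed and handed out (V2, D-31 to D-29). Its list includes "Recording of vital signs and targeted physical exam if indicated" and "Re-verification of eligibility criteria", but no pregnancy test. In the Appendix A grid the pregnancy-test row is marked at V1 and V3, conditionally marked at V4 to V10, and empty at V2.

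Section 11 adds general safeguards. Inclusion criterion 3 says: "Women of child bearing potential must agree to use effective birth control for the first 3 months of the study". It also asks for a documented negative test, but ties that to vaccination. Exclusion criterion 7 is: "Pregnancy or breast feeding, or plans to become pregnant in the first 3 months of study participation". The extra criteria for the statin arm do not mention a pregnancy test.

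**The concern.** The footnote commits the trial to a test that the grid and the visit list do not carry. The visit affected is the one at which it matters most: atorvastatin 80 mg is dispensed there, and Section 12 gives possible fetal harm from this drug class as a reason for excluding pregnant women.

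If the grid and Section 6.2 are followed literally, a participant of child-bearing potential can start daily dosing on the screening test alone and not be tested again until D1. A pregnancy too early to detect at screening, or begun between screening and V2, could then be exposed for about four weeks before the next required test. There is also a compliance problem: with the footnote and its own table in disagreement, nobody can say whether an untested V2 is a protocol deviation.

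**Working it through.** The plan gives no figure to reproduce. The check has two parts: a comparison of the texts, and the spacing of tests implied by the visit windows.

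**1. The texts side by side**

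| Occasion in the footnote | Pregnancy-test row, Appendix A | Procedure text |
|---|---|---|
| Screening (V1) | x | Section 6.1.2: itemised |
| Before statin initiation (V2) | blank | Section 6.2: not among the 8 items |
| Before vaccination (V3, D1) | x | Section 6.4: negative result required |

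The blank is not a shifted column. The header has 11 columns (V1 to V10 plus the phone call), and the row has 11 cells: x, blank, x, seven (x), blank. V2 is therefore the only clinic visit without a mark. Even V9 and V10, which fall after the statin course has ended, carry a conditional mark.

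Vital signs, which the same footnote sentence governs, do reach V2: there is a conditional mark in the grid and an item in Section 6.2.

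**2. Spacing of tests within the windows**

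Inputs: V1 is D-60 to D-32 and V2 is D-31 to D-29 (Sections 6.1 and 6.2, Appendix A). V3 is D1 (Section 6.4).

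Age of the screening test at V2:
- shortest: 32 − 31 = 1 day
- longest: 60 − 29 = 31 days

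The interval to D1 depends on whether the calendar has a Day 0, which the protocol does not say.

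| Interval | No Day 0 | With Day 0 |
|---|---|---|
| V2 to D1 | 29 to 31 days | 30 to 32 days |
| V1 to D1 (gap between required tests if the grid is followed) | 32 to 60 days | 33 to 61 days |

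These are not hard limits, because Appendix A allows visits outside the window at the investigator's discretion. Appendix A gives the clinical labs a validity of 30 days; it gives no such limit for the pregnancy test.

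**3. Whether another provision requires the test**

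- Re-verification of eligibility at V2 covers exclusion 7 in principle, but does not say how pregnancy is to be ruled out.
- The only test named in the criteria is in inclusion 3, and a D1 test satisfies it.
- The statin-arm criteria in Section 11 require none.

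The footnote is therefore the only place that requires a test before dosing.

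**The case against.** The strongest reply is that the protocol already requires the test. The footnote sits directly under the grid, so what is missing is a mark and a bullet, not a safeguard. Nothing in the documents shows that staff would overlook the footnote. A licensed provider must complete the prescription form at V2, interim history and eligibility are reviewed there, contraception is required, and pregnancy leads to withdrawal (Section 16.5). It is fair to conclude that the risk is reduced and that the long gap between tests arises only if the footnote is not acted on. But none of these other steps calls for a test, and a grid that contradicts its own footnote is a poor basis for relying on the footnote.

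A second reply reads the footnote as naming two occasions: the screening day, which precedes statin initiation, and the time before vaccination. That would match the row and the silence of Section 6.2. The reading is possible, but it makes the middle item redundant.

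A third reply is that the vital-signs row is weak evidence, since it is conditionally marked at every visit, including seven that the footnote does not name. This stands for the grid. The vital-signs item in Section 6.2 still counts.

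Finally, the table was read from a PDF, so a lost mark cannot be wholly excluded. The omission from Section 6.2 is in running text and does not depend on the table.

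**Conclusion.** The inconsistency is real and should be fixed. On its natural reading the footnote requires a pregnancy test before atorvastatin is started; the grid and Section 6.2 do not carry it, and no other provision does.

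The safety-relevant figure is the age of the last scheduled test at the first dose: 1 to 31 days, assuming that visits stay within their windows and that the first dose is taken at about V2. Those concerned are the participants of child-bearing potential among the 30 planned for the statin arm; the protocol does not give their number. Existing safeguards lower the risk but do not replace a test. The primary endpoint, the sample size and the analysis are unaffected.

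**What to change.** 1. In Appendix A, mark the V2 cell of the pregnancy-test row with x, as at V1 and V3.
2. In Section 6.2, add an item before the prescription step: negative urine pregnancy test before dispensing, for participants of child-bearing potential.
3. In the statin-arm criteria of Section 11, add a negative test before statin initiation. This overlaps largely with exclusion 7 and is not needed to remove the contradiction, but it makes the result a documented condition of dosing.

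Inclusion criterion 3 should stay as it is: it applies to both arms and is properly tied to vaccination.

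The cost is one schedule mark, one list item and, if adopted, one criterion, plus one urine test per applicable statin-arm participant. That is at most 30 tests if enrolment meets the plan, with any replacements adding to it. The visit already takes place, and the footnote already commits to the test.
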